8.7. Losses to follow-up

If contact cannot be made and the participant has not withdrawn their consent to participation in the trial, outcome data will be obtained from medical records and/or NHS England where possible. If it is not possible to obtain the primary outcome the participant will be designated as lost to follow-up for the primary outcome.

9. Adverse Event Reporting

9.1. Definitions

Adverse Event (AE)	
Any untoward medical occurrence in a clinical trial participant administered a medicinal product and which does not necessarily have a causal relationship with this treatment.
 
An AE can therefore be any unfavourable and unintended sign (including abnormal laboratory findings), symptom or disease temporally associated with the use of an investigational medicinal product, whether or not related to the investigational medicinal product.

Adverse Reaction (AR)	
All untoward and unintended responses to an IMP related to any dose administered.
 
An AE judged by either the reporting Investigator or Sponsor as having causal relationship to the IMP qualifies as an AR. The expression reasonable causal relationship means to convey in general that there is evidence or argument to suggest a causal relationship.

Trial name:	Premature Ovarian Insufficiency Study of Effectiveness of hormonal therapy	Protocol version:	4.0	date:	01 Oct 2024	Page:	35
-------------	--	-------------------	-----	-------	-------------	-------	----

Serious Adverse Event (SAE)
	
Any untoward medical occurrence or effect that:
 
 • Results in death • Is life-threatening* • Requires hospitalisation or prolongation of existing hospitalisation • Results in persistent or significant disability or incapacity • Is a congenital anomaly/birth defect • Or is otherwise considered medically significant by the Investigator** 
The term severe is often used to describe the intensity (severity) of a specific event. This is not the same as serious, which is based on participants/event outcome or action criteria.
 
* Life threatening in the definition of an SAE refers to an event in which the participant was at risk of death at the time of the event; it does not refer to an event that hypothetically might have caused death if it were more severe.
 
** Medical judgment should be exercised in deciding whether an AE is serious in other situations. Important AEs that are not immediately life threatening or do not result in death or hospitalisation but may jeopardise the participant or may require intervention to prevent one of the other outcomes listed in the definition above, should be considered serious.

Serious Adverse Reaction (SAR)
	
An Adverse Reaction which also meets the definition of a Serious Adverse Event


Unexpected Adverse Reaction (UAR)
	
An AR, the nature or severity of which is not consistent with the applicable product information (e.g. Investigator Brochure for an unapproved IMP or Summary of Product Characteristics (SmPC) for a licensed product).
 
When the outcome of an AR is not consistent with the applicable product information the AR should be considered unexpected.

Suspected Unexpected Serious Adverse Reaction (SUSAR)
	
A SAR that is unexpected i.e. the nature, or severity of the event is not consistent with the applicable product information.
 
A SUSAR should meet the definition of an AR, UAR and SAR.

9.2. Adverse Events and reporting requirements/procedures

The collection and reporting of Adverse Events (AEs) will be in accordance with the Medicines for Human Use Clinical Trials Regulations 2004 (and subsequent amendments).

All IMPs (HRT and COC) being used in this trial are licensed and have well characterised safety profiles.

All preparations of HRT used in this trial are licensed for use for oestrogen deficiency symptoms in post- and peri-menopausal women.

Whilst the COC is licensed as an oral contraceptive it is not licensed specifically for treating oestrogen deficiency and POI. It is however widely, prescribed for the treatment of POI; this off-label use is standard practice and all treatments used in the trial have well-established safety profiles.

In order to provide secondary outcome data about the adverse events associated with the use of the COC or HRT, only specified adverse events will be collected.

The following expected AEs will be participant-reported and collected using a questionnaire at 3, 6, 12 months and yearly up to 5 years, depending on the point at which the participant joins the trial. If a

Trial name:
	
Premature Ovarian Insufficiency Study of Effectiveness of hormonal therapy
	
Protocol version:
	
4.0
	
date:
	
01 Oct 2024
	
Page:
	
36

--------------------	---	--------------------------	------------	--------------	--------------------	--------------	-----------

clinic visit is not possible or a participant fails to attend, questionnaires will be provided to participants electronically so they can be completed remotely.

Participants will be asked at each follow-up visit if they have experienced any of the following:

- Unscheduled bleeding
- Breast pain
- Nausea
- Headaches
- Skin or hair changes (acne/facial spots, greasy or oily skin, hair loss/hair thinning, hirsutism (=excessive hair growth on face or body))
- Dysmenorrhoea (period pains)
- Menorrhagia (heavy periods)
- Premenstrual syndrome (PMS)
- VTE or pulmonary embolism (PE)
- Broken bone(s)

Where any of the above events result in an admission to hospital or prolongation of a hospital stay this will also require reporting on a SAE form by the Principal Investigator or delegate (see section 9.3).

Adverse events will be coded using the Medical Dictionary for Regulatory Activities (MedDRA) as per NCTU standard practice.

9.3.Serious Adverse Events and reporting requirements

Investigators will report all AEs that they become aware of that meet the definition of an SAE, including those adverse events collected via patient questionnaire as mentioned in section 9.2.

AEs defined as serious, and which require reporting as an SAE should be reported on an SAE form. When completing the form, the Investigator will be asked to define the causality and severity of the AE. The SAE form must be sent to the NCTU as soon as possible and no later than 24 hours after first becoming aware of the event (or obtaining the follow-up information from the participant).

On receipt NCTU will allocate each SAE a unique reference number which will be forwarded to the site as proof of receipt within 1 working day. If confirmation is not received within 1 working day sites should contact the NCTU. The SAE reference number will be quoted on all correspondence and follow-up reports regarding the SAE and filed with the actual SAE in the Site File and TMF.

Sites

For SAE Forms completed by someone other than the Investigator, the Investigator will be required to countersign the original SAE Form to confirm agreement with the causality and severity assessments. The form should then be returned to NCTU and a copy kept in the Site File. Investigators should also report SAEs to their own Trust in accordance with local practice.

On becoming aware that a participant has experienced an SAE, the Investigator (or delegate) must complete, date and sign a SAE form. The form should be e-mailed to NCTU using the following e-mail address:

FOR SAE REPORTING ONLY: [contact]

Trial name:	Premature Ovarian Insufficiency Study of Effectiveness of hormonal therapy	Protocol version:	4.0	date:	01 Oct 2024	Page:	37
-------------	--	-------------------	-----	-------	-------------	-------	----

NCTU

On receipt of an SAE Form seriousness and causality will be reviewed independently by the medical monitor responsible for determining causality assessments. An SAE judged by the Investigator or medical monitor (in this case the CI), to have a reasonable causal relationship with the trial medication will be regarded as a Serious Adverse Reaction (SAR). The medical monitor will also assess all SARs for expectedness. If the event meets the definition of a SAR that is unexpected (i.e. is not defined in the Reference Safety Information (RSI) –see Section 9.4) it will be classified as a SUSAR.

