1.2.3. Choice of treatment

Two preparations are widely prescribed in the UK as oestrogen replacement for women with POI, HRT and COC. HRT is based on physiological oestrogen (17β oestradiol) and usually contains synthetic progestogen although alternatives (natural progesterone, intrauterine progestogen) are available; treatment may be oral or transdermal. The COC contains ethinylloestradiol, a synthetic oestrogen with significant metabolic impact, and synthetic progestogen.

The trial is a two-group design, with participants randomised to receive either HRT or the COC. The type and dose of oestrogen is specified. The type and dose of progestogen is specified, as far as practicable given the preparations available, to standardise the treatments used.

In view of the variety of available hormonal preparations, some with added contraceptive properties, it is neither practical nor ethical to blind the treatments to the women or treating clinicians.

HRT:

The trial mandates that the HRT preparation contains 17β-oestradiol. This is available via oral and transdermal routes, the latter being the preferred choice of half of the clinicians surveyed when designing the trial. However, transdermal HRT may not be as acceptable to women as oral tablets, and patches may cause skin irritation, acknowledged by our patient survey, so the trial will not specify which formulation is used. It is acknowledged that the pharmacodynamics differ. Therefore, it is required that the **oestradiol daily starting dose is 2mg orally or 50µg patch or 1.5mg gel transdermally** (these are considered clinically equivalent). Dose will not be titrated by serum oestradiol measurement as this is not done in clinical practice and of limited value in oral therapy.

Women with POI and an intact uterus require progestogen to protect against endometrial hyperplasia; progestogen may be given cyclically or continuously. This will not be mandated, as the trial design survey indicated that the formulation used was predicated on the need for contraception or other patient preferences, with 15 out of 42 of HRT prescribers surveyed offering the levonorgestrel-releasing intrauterine system (LNG-IUS) and the same number oral micronised progesterone. Women who are not using the LNG-IUS will be informed of the small chance of spontaneous pregnancy in POI and advised to use non-hormonal contraception if required.

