2.1.2. Secondary objectives -effectiveness

- To assess the relative effectiveness, of HRT (any route) compared to the COC on menopausal symptoms, quality of life, sexual functioning, weight, and blood pressure.
- To assess the effect of treatment with HRT (any route) compared to COC on adherence with treatment, pregnancy outcome, side effects and serious adverse events.
- To assess the relative effectiveness of oral and transdermal HRT, compared to the COC in terms of BMD, blood pressure and menopausal symptoms.
- To compare the prevalence of bone fractures, diagnosis of cardiovascular disease, cancer, cognitive impairment and mortality between women treated with HRT (any route) and those treated with COC.

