7.1.1. HRT

Women randomised to receive treatment with HRT should be prescribed oestradiol in a **daily dose** of 2mg orally, or a 50µg patch, or 1.5mg of gel, given continuously.

Women with a uterus will also be prescribed progestogen, taken cyclically or continuously. The formulation is not mandated. The preferred oral formulation is oestradiol 2mg with dydrogesterone 10mg (Femoston 2/10), and the preferred transdermal formulation is oestradiol 50µg with norethisterone 170µg patch (Evorel Sequi). Alternative formulations can be prescribed if required but must contain oestradiol as mandated above, for example oestradiol gel with micronised progesterone or LNG-IUS.

Women who are not using the LNG-IUS will be advised to use non-hormonal contraception if required.

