7.1.2. COC

Women allocated the COC should be prescribed 30µg ethinyloestradiol with 150µg levonorgestrel (Microgynon 30 or equivalent) as an extended regimen; the suggested regimen is 63 days with 7 days hormone-free interval. Alternative formulations can be prescribed if required but must contain 30µg ethinyloestradiol in a monophasic formulation.

Use of a contraceptive patch or ring is not permitted.

Table 2: Summary of treatment options for initiating randomised treatment

Treatment Group	Permitted route(s) of administration	Formulation/Specified dose	Administration/additional information
COC	Oral	Monophasic tablets containing 30µg ethinyloestradiol	Tricycling for 63 days of tablets followed by a 4-7 day hormone-free interval, or flexible extended use, taking continuously with short breaks of 3-4 days if breakthrough bleeding occurs. The preferred regimen is tricycling for 63 days of tablets followed by a 7-day hormone-free interval.
HRT	Oral	Containing 17β-oestradiol. Starting dose: 2mg daily.	Women with POI and an intact uterus require progestogen to protect against endometrial hyperplasia; progestogen may be given cyclically or continuously.
	Transdermal	Containing 17β-oestradiol. Starting dose: Patch: 50µg oestradiol daily Gel: 1.5mg oestradiol daily	

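### The closed adverse-event list has no item for patch-site skin irritation, which the protocol itself names as a drawback of patches, so the side-effect comparison cannot show it

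*Protocol*

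**What the plan says.** Section 2.1.2 makes a comparison of HRT (any route) with the COC "on adherence with treatment, pregnancy outcome, side effects and serious adverse events" a secondary objective.

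Section 9.2 limits what is gathered for it: "only specified adverse events will be collected". It describes the listed events as expected, and has participants report them by questionnaire at 3, 6 and 12 months and yearly after that. There are ten prompts: unscheduled bleeding, breast pain, nausea, headaches, skin or hair changes, dysmenorrhoea, menorrhagia, premenstrual syndrome, VTE or pulmonary embolism, and broken bones. The skin prompt carries its own definition: "Skin or hair changes (acne/facial spots, greasy or oily skin, hair loss/hair thinning, hirsutism (=excessive hair growth on face or body".

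Section 1.2.3, explaining why the HRT product is left open, says that "patches may cause skin irritation, acknowledged by our patient survey, so the trial will not specify which formulation is used".

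Section 7.1.1 names a patch as the preferred transdermal product ("the preferred transdermal formulation is oestradiol" with norethisterone, as a patch). Section 7.1.2 says of the COC group: "Use of a contraceptive patch or ring is not permitted".

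Section 13.3 says adverse events are summarised descriptively only, by allocated group and by treatment received.

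**The concern.** The protocol identifies a tolerability problem with one of its trial products and uses it to justify a design decision. It then draws up a closed list of expected side effects that leaves the problem out. The omission falls on one treatment: patches belong to HRT and are not permitted as a form of the COC.

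What is at stake is the completeness of the side-effect table for the second secondary objective. Section 1.1 says women need information to choose between two acceptable treatments. A table with no line for an acknowledged drawback of patches serves that purpose less well. The gap also touches the reading of adherence, because irritation is a plausible reason for leaving the patch. An analysis plan cannot repair this later, since the data would not have been collected.

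**Working it through.** No stated figure depends on this point, so there is none to reproduce. The check is a comparison of sections, followed by a rough indication of scale.

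**Is the effect collected anywhere?**

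- *Section 9.2 list.* No prompt mentions irritation or an application site. The bracket after the skin prompt confines it to acne or spots, greasy skin, hair loss or thinning, and hirsutism.
- *Section 2.2.2.* It mentions skin or hair changes without the bracket but refers to Section 9.2, where the term is defined.
- *Sections 9.1 and 9.3 (serious events).* These cover events that meet a seriousness criterion. Patch irritation would seldom do so.
- *Sections 2.2.2, 7.3 and 7.6 (change or cessation of treatment, satisfaction).* These record that a woman changed treatment or was dissatisfied. They do not count irritation as a side effect, and they miss women who put up with it. The protocol does not say whether a reason for change is recorded.
- *Section 9.5.* It speaks of documenting adverse events other than those listed in Section 9.2. That conflicts with the closed list, but it provides no questionnaire item or other route for non-serious events.

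**In which group can it arise?** Under allocated treatment, only HRT involves a patch (Sections 7.1.1 and 7.1.2). Section 7.3 allows switching without a protocol deviation, so a woman allocated to the COC could later use an HRT patch. The effect is therefore specific to HRT as received, and only largely so by allocated group.

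**Scale, for illustration only.**

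Inputs:
- Women in the HRT group: 380 / 2 = 190 (Section 13.1.1, 1:1 allocation).
- Transdermal share: 20% to 80%. Section 13.1.1, in the power statement for the original sample size, assumes that one route has 20% to 50%, so the other has 50% to 80%.
- Patch share of transdermal use: 50% to 100%, **assumed**.
- Irritation rate among patch users: 5% to 20%, **assumed**.

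Formula: women affected = 190 × transdermal share × patch share × irritation rate.

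| Case | Calculation | Women | Share of HRT group |
|---|---|---|---|
| Low | 190 × 0.20 × 0.50 × 0.05 | 0.95, about 1 | 0.5% |
| Middle | 190 × 0.50 × 1.00 × 0.10 | 9.5, about 10 | 5% |
| High | 190 × 0.80 × 1.00 × 0.20 | 30.4, about 30 | 16% |

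The range is wide because two of the three multipliers are assumptions.

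**The case against.** The strongest reply is that targeted collection is a deliberate and reasonable choice. The products are licensed with well-known safety profiles, and Section 7.2.2 classes the trial as low risk (Type A). Adverse events are descriptive, and leaving out one item does not distort the comparison of any item that is listed. Women who give up patches will appear as treatment changes, and dissatisfaction will appear on the Likert scale. Section 9.5 and the looser wording of Section 2.2.2 suggest the list may not be fully closed. The transdermal share is unknown, because route follows participant preference (Section 6.2).

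Much of this stands. A reader might infer that the omission tilts the whole side-effect comparison in favour of HRT. The documents do not support that. The protocol defines no total side-effect count or tolerability score, and whether unlisted effects of the COC would offset this one cannot be judged from the text. A reader might also take the preference of half the surveyed clinicians for the transdermal route (Section 1.2.3) as expected use and derive a firm percentage of women affected. That survey result is not a forecast of use, and the protocol gives no irritation rate. Finally, the protocol attributes irritation to patches; it does not mention it for gel.

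The gap itself remains. A short list of expected effects is defensible, but this one omits an effect the same document already acknowledges, and none of the indirect routes counts it.

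**Conclusion.** The point holds in limited form. As written, the side-effect comparison cannot show patch-site irritation, an effect the protocol names and one that arises essentially only with HRT as received. Comparisons of the ten listed prompts, the primary outcome and all formal tests are unaffected. For this single event, omission can only understate what women using patches experience; no net direction across all unlisted effects is established.

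The size cannot be derived from the protocol. About 1 to 30 women in the HRT group is an illustration that rests on the assumed patch shares and irritation rates above. The change is worth making because it is cheap and because data not collected cannot be recovered at analysis.

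**What to change.** 1. Add one item to the questionnaire list in Section 9.2 and to the side effects named in Section 2.2.2, for example: skin irritation at the patch (or other application) site, if used. Including other application sites is a precaution that goes beyond what the protocol states about patches.
2. Ask it at every remaining follow-up visit. Under Section 8.1 follow-up runs until the last participant randomised reaches 2 years.
3. Report it descriptively by allocated group and by treatment received, with the date collection began and the reduced denominator shown.
4. Reconcile Section 9.5, which refers to adverse events outside the Section 9.2 list, with the statement that only specified events are collected.

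The cost is an amendment and one extra line on an existing questionnaire and eCRF page. Visits already completed will lack the item, so early irritation in women recruited first is lost. If the item is not added, the report should state that the side-effect comparison does not cover patch-site effects.

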1.1. Background

Premature ovarian insufficiency (POI) is a clinical syndrome defined by the loss of ovarian activity before the age of 40 years, which affects at least 1 in 100 women⁴. Although the cause is unknown in most women, it can be familial (in 10%) or associated with autoimmunity or genetic conditions (e.g. Turner syndrome). POI can be a result of treatment (oophorectomy, chemotherapy, or pelvic radiotherapy) and is increasing in young cancer survivors⁵.

National Institute for Health and Care Excellence (NICE) guidelines recommend that diagnosis is made by both a history of menopausal symptoms, including amenorrhoea or infrequent periods, and elevated follicle-stimulating hormone (FSH) levels on two blood samples taken 4-6 weeks apart⁶. Other markers of ovarian reserve, such as anti-Mullerian hormone and antral follicle count on transvaginal ultrasound scan, are not currently recommended as diagnostic tests for POI.

POI is associated with low levels of circulating oestrogen, although ovarian function can fluctuate in some women before complete cessation. Symptoms of oestrogen deficiency include hot flushes and night sweats, vaginal dryness causing painful intercourse, low libido, low energy levels, sleep disturbance, lack of concentration, muscle and joint aches and stiffness, skin/hair changes and labile mood.

Long-term outcomes of oestrogen deficiency include loss of BMD, potentially leading to early onset of osteoporosis, fracture and disability, as seen in post-menopausal women⁷; increased risk of cardiovascular disease (CVD) of earlier onset⁸, reduced life expectancy^{4,9}; and possibly an increased risk of degenerative neurological disease (Parkinson’s disease, cognitive impairment)¹⁰.

Women with POI are provided with advice regarding a healthy lifestyle (involving weight-bearing exercise, avoidance of smoking, maintenance of a normal body weight, and the recommended dietary intake of calcium and vitamin D) for promotion of bone health and reduction of CVD risk. However, lifestyle measures alone are insufficient and all professional bodies recommend long-term systemic hormone treatment at least until the age of natural menopause^{6,11} to improve symptoms, to maintain bone health and prevent osteoporosis, and to reduce future CVD risk; topical oestrogen (vaginal pessaries or cream) can be used in addition to treat genito-urinary symptoms.

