8.1. Summary of assessments

A summary of the trial procedures and assessments is shown in Table 3. A detailed description of each assessment is provided in Section 8.2.

Follow-up assessments will follow the schedule shown in Table 3 until the final participant randomised has completed their 2-year follow-up assessment. This means that those participants recruited early in the trial will provide data annually up to 5 years.

Table 3: Summary of trial procedures and assessments

	Timepoint											
	Pre-enrolment & Screening	BL	0	Follow-up**						4y	5y	
				3m	6m	1y	2y	3y				
ENROLMENT:												
Patient identification	X											
Informed consent	X											
Washout (if needed)	X											
Confirm eligibility		X										
Patient demographics		X										
Lifestyle factors e.g. smoking, alcohol, exercise habits		X		X	X	X	X	X	X	X	X	
Use of medication e.g. prescribed, complementary and supplements		X		X	X	X	X	X	X	X	X	
Randomisation			X									
TREATMENT / INTERVENTION:												
HRT												
COC												
ASSESSMENTS:												
BMD (DEXA scan) lumbar spine and hip		X				X	X				X	
Quality of life (MENQOL-I)		X		X	X	X	X	X	X	X	X	
Sexual function (SAQ)		X		X	X	X	X	X	X	X	X	
Work productivity (WPAI)		X		X	X	X	X	X	X	X	X	
Blood pressure and weight		X		X	X	X	X	X	X	X	X	
Height		X										

Trial name:	Premature Ovarian Insufficiency Study of Effectiveness of hormonal therapy	Protocol version:	4.0	date:	01 Oct 2024	Page:	30
-------------	--	-------------------	-----	-------	-------------	-------	----

Blood and urine samples for bone biomarkers*		X		X		X				
Blood sample for CVD biomarkers*		X		X		X	X	X	X	X
Karyotype analysis* (if clinically appropriate and if not done prior to entering the trial).		X								
Pregnancy status and outcome		X		X	X	X	X	X	X	X
Adverse effects of treatment				X	X	X	X	X	X	X
Change/cessation/satisfaction of treatment				X	X	X	X	X	X	X

*only performed at selected sites

m = months, y = years, BL = baseline

** Duration of participation will be up to 5 years, for a minimum duration of 2 years

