8.2. Schedule of Assessments

8.2.1. Enrolment and baseline

a) Identify potentially eligible patient

All potentially eligible patients should be approached and provided with information about the trial. This information will be entered onto the patient screening/enrolment log at each recruiting site. Patients that decline participation are not obliged to give a reason, however this will be recorded where this is known. Sites will be required to provide a summary of screening data on an ongoing basis during the recruitment period which will be reviewed regularly by the Trial Management Group (TMG) and oversight committees.

b) Informed Consent

Informed consent will be obtained as described in section 5. If a patient requires a washout period then eligibility will need to be re-confirmed prior to collecting baseline data.

c) Washout

Eligible women who are already on COC/HRT/testosterone treatment are required to stop treatment for a washout period of a minimum of 4 weeks. This is to ensure a return to pre-treatment hormone levels before performing baseline assessments.

d) Confirm Eligibility

Eligibility will be confirmed by the principal investigator or delegated trial doctor using the eligibility checklist form once informed consent and baseline data have been obtained.

e) Baseline data collection

After informed consent (and washout if applicable), baseline visit data will be collected by a member of the site research team and will include:

1. Patient demographics
2. Lifestyle factors e.g. smoking, alcohol, exercise habits
3. Use of medication e.g. prescribed, complementary and supplements
4. Pregnancy and breastfeeding
5. BMD (DEXA bone density measurement of lumbar spine and hip)
6. Quality of life (MENQOL-I questionnaire)
7. Sexual function (SAQ)
8. Work productivity (WPAI questionnaire)
9. Blood pressure (BP) and weight (refer to details below for BP measurement)
10. Height (measured at visit)
11. Blood and/or urine samples for bone and CVD biomarkers (selected sites only)

Trial name:	Premature Ovarian Insufficiency Study of Effectiveness of hormonal therapy	Protocol version:	4.0	date:	01 Oct 2024	Page:	31
-------------	--	-------------------	-----	-------	-------------	-------	----

12. Karyotype analysis (selected sites only and if clinically appropriate and not done prior to entering trial.

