- Adjustment for any other baseline variable (if applicable) with marked imbalance between the two treatment groups

Supplementary analyses for the primary outcome will investigate potential effects of compliance with allocated treatment using complier average causal effect (CACE) analysis (or per-protocol analysis should there be high crossover rates making CACE identification impossible) and estimate an overall time-averaged between-group effect over the 2 years to compare the overall rate of change in BMD between groups.

Main analyses of secondary outcomes will be based on intention-to-treat, analysing participants in the groups to which they were randomised, regardless of adherence with allocation. Sensitivity analyses (as described for the primary outcome) may also be performed for key secondary outcomes such as blood pressure, MENQOL-I, and BMD at 1 year and 2 years. Ordered logistic regression models will be used to compare the total lumbar spine and hip T-score categories (≤ -2.5 , > -2.5 to ≤ -1 , > -1) between groups, adjusted for the minimisation variables; however, should there be only a small number of participants in one of the categories then categories will be collapsed into two for analysis and logistic regression used. Between-group comparison of secondary outcomes will be based on an appropriate regression for the outcome adjusted for the minimisation variables and baseline outcome measure for continuous variables if available. For repeated measures, appropriate mixed-effect models for the outcome (linear for continuous outcomes and logistic for binary), adjusted for the minimisation variables, will be used to estimate the difference between groups at each time point. Supplementary analysis of key secondary outcomes may also be conducted according to actual treatment used if the percentage of women who stop using their allocated treatment or switch to the other treatment is high.

Adverse events will be presented descriptively only and will be summarised according to both the allocated group and the treatment received.

Trial name:	Premature Ovarian Insufficiency Study of Effectiveness of hormonal therapy	Protocol version:	4.0	date:	01 Oct 2024	Page:	44
-------------	--	-------------------	-----	-------	-------------	-------	----

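### The side-effect checklist has no baseline administration, so as described the trial cannot separate new complaints from those present before treatment

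*Protocol*

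**What the plan says.** Section 9.2 sets the timing: "The following expected AEs will be participant-reported and collected using a questionnaire at 3, 6, 12 months and yearly up to 5 years". The checklist opens with "Participants will be asked at each follow-up visit if they have experienced any of the following". As described, the question is not limited to new or worsened complaints. One entry is "Skin or hair changes (acne/facial spots, greasy or oily skin, hair loss/hair thinning, hirsutism"; others include headaches, nausea and breast pain.

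In Table 3 (section 8.1) the matching row is labelled "Adverse effects of treatment". It is marked from 3 months onward and blank at baseline. MENQOL-I, SAQ, WPAI, blood pressure and pregnancy status all carry a baseline mark. Section 8.2.1(e) says that "baseline visit data will be collected by a member of the site research team and will include" twelve items, and the checklist is not among them.

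The symptoms of oestrogen deficiency in section 1.1 include "lack of concentration, muscle and joint aches and stiffness, skin/hair changes and labile mood".

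Side effects belong to a secondary objective (section 2.1.2), and several of these complaints are named within a secondary outcome (section 2.2.2). Section 13.3 plans a descriptive presentation only, "summarised according to both the allocated group and the treatment received".

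**The concern.** At least one complaint has two roles. Skin or hair changes are a symptom of the condition before randomisation and an expected adverse event afterwards. Headaches, nausea and breast pain can also precede treatment. With no baseline answer, a woman whose complaint is unchanged and a woman whose complaint began on treatment may give the same reply at 3 months.

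Two results are exposed. The first is the absolute frequency of each complaint, which Table 3 labels as an effect of treatment. The second is the summary by treatment received, where randomisation gives no protection: a woman may choose, avoid or leave a preparation because of a complaint she already had. Section 7.3 allows switching without counting it as a deviation and expects adherence to fall over time, so the received-treatment groups will differ from the randomised ones.

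The gap lies in data collection. A statistical analysis plan cannot supply an answer that was never asked for.

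**Working it through.** **Check of the text.** No protocol figure is at stake, so the relevant places are set side by side.

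| Place | Content |
|---|---|
| 9.2 | Checklist at 3, 6 and 12 months, then yearly |
| Table 3 | Baseline blank in the adverse-effects row |
| 8.2.1(e) | Twelve baseline items, no checklist |
| 1.1 and 9.2 | Skin or hair changes appear in both the symptom list and the side-effect list |
| 9.5 | The rule that reporting begins with treatment exempts the 9.2 events |
| 7.1 and 8.2.1(c) | At least 4 weeks of washout, so that baseline reflects the untreated state |

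The baseline visit is therefore designed to record untreated symptoms, yet this checklist is left out. No onset rule stated elsewhere fills the gap.

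**Illustration of size. All rates are assumed; none comes from the protocol.** Let b be the share with the complaint at baseline, k the share of those who still report it, and p the new-onset rate among the rest. Then

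observed rate = b × k + (1 − b) × p.

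*Case A: k = 0.60, p = 5% and 10%.*
- b = 30%: 0.18 + 0.70 × 0.05 = 21.5%, and 0.18 + 0.70 × 0.10 = 25.0%. The difference is 3.5 points and the ratio 1.16.
- b = 15%: 0.09 + 0.85 × 0.05 = 13.25%, and 0.09 + 0.85 × 0.10 = 17.5%. The difference is 4.25 points and the ratio 1.32.

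*Case B: k = 1, p = 10% and 20%.*
- b = 10%: 19% and 28%. The difference is 9 points and the ratio 1.47.
- b = 30%: 37% and 44%. The difference is 7 points and the ratio 1.19.

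The new-onset ratio is 2.0 in every case.

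**What the illustration shows about bias.** With equal b and k in both groups, the observed difference is (1 − b) times the new-onset difference: 5 × 0.70 = 3.5 points, or 10 × 0.90 = 9 points. That is dilution, and 3.5 points is still a correct difference in complaints among all women. What is inflated is each group's rate when it is read as a treatment effect. In Case A with b = 30%, existing complaints make up 18/21.5 = 84% of reports in the lower-rate group and 18/25 = 72% in the higher-rate group. In Case B with b = 10%, the shares are 0.10/0.19 = 53% and 0.10/0.28 = 36%.

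**Chance imbalance.** With 304 analysed (section 13.1.1), or 152 per group, the 95% range for a chance difference in baseline prevalence is ±1.96 × √(2b(1 − b)/152). This is ±6.7 points at b = 10% and ±10.3 points at b = 30%. As described, such an imbalance could not be seen.

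**How many women a change could reach.** The protocol gives no accrual to date. If accrual were uniform over the 57 months and the change took effect at the month-36 review, 380 × (57 − 36)/57 = 140 women would remain.

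**The case against.** Much of the opposing case is sound.

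- **The questionnaire is not in the document.** Its recall wording might limit replies to new complaints, and the adverse event definition in section 9.1 requires a temporal association with the product. A reader might infer that existing complaints are certainly counted as adverse effects. The text supports only that nothing described prevents it.
- **The randomised comparison.** A reader might infer bias between the allocated groups. Randomisation balances prior complaints in expectation, so the documents do not support that. The fall in the ratio comes partly from the choice of scale, and every input is assumed.
- **Adjustment.** A reader might infer that a planned analysis loses precision. Adverse events are to be presented descriptively, so no planned model or test is affected.
- **Breadth.** Not every item is exposed. Diagnosis rests on a history that includes absent or infrequent periods, and baseline follows washout, so heavy or painful periods and premenstrual syndrome are unlikely to be common then. Thromboembolism and fractures can be dated. Only skin or hair changes are tied to the condition by the text.
- **Symptom relief.** MENQOL-I, with its physical domain, is collected at baseline and at every follow-up. It may overlap with some items, but the protocol does not say which.
- **Yield.** Even with 140 women remaining, 240 of 380 (63%) would have no baseline answer. At 30% prevalence about 49 per group (70 × 0.70) would be free of the complaint at baseline, before attrition. Retention was Amber at the first feasibility review, so extra burden counts.

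These points limit the weight of the concern. They do not remove the missing baseline answer, the possible overstatement of absolute rates or the exposure of the summary by treatment received.

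**Conclusion.** The point holds as a modest and inexpensive improvement. As described, the checklist cannot separate new complaints from existing ones, mainly for skin or hair changes, headaches, nausea and breast pain. The summary by allocated group is diluted but not systematically biased. The absolute rates may be overstated, and the summary by treatment received may be confounded by complaints that preceded treatment. The real size is unknown. On the assumed inputs, existing complaints could form between about a third and more than four fifths of reports. These figures illustrate the mechanism and do not estimate what this trial will see. The conclusion also assumes that the questionnaire does not itself restrict replies to new complaints. The primary BMD outcome is not touched.

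**What to change.** Add the symptom items of section 9.2, without thromboembolism and fractures, to section 8.2.1(e) and to the baseline column of Table 3. Ask them after washout and before randomisation, for all women still to be randomised.

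Keep the planned descriptive tables for all women. Beside them, report new-onset complaints by allocated group and by treatment received, among women with a baseline answer only, and label the two definitions clearly. Report worsening only if a severity grade is recorded at both times; the checklist as described records only whether an item was experienced.

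Do not use a missing-indicator for absent baseline answers in the summary by treatment received, because its justification depends on randomisation. A baseline answer also cannot correct for switching prompted by a complaint that began on treatment, so that summary should be interpreted with this in mind.

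State as a limitation that women already randomised have no baseline answer, and give the number.

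The cost is one short extra form at an existing visit, a minor amendment, and baseline data for only part of the sample.
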